10.1.5. Data Quality Assurance

- All subject data relating to the study will be recorded on printed or electronic eCRF unless transmitted to the Sponsor or designee electronically (eg, laboratory data). The

- Investigator is responsible for verifying that data entries are accurate and correct by physically or electronically signing the eCRF.
- The Investigator must maintain accurate documentation (source data) that supports the information entered in the eCRF.
 - The Investigator must permit study-related monitoring, audits, IRB/IEC review, and regulatory agency inspections and provide direct access to source data documents.
 - Monitoring details describing strategy (eg, risk-based initiatives in operations and quality such as Risk Management and Mitigation Strategies and Analytical Risk-Based Monitoring), methods, responsibilities and requirements, including handling of noncompliance issues and monitoring techniques (central, remote, or on-site monitoring) are provided in the Monitoring Plan.
 - The Sponsor or designee is responsible for the data management of this study including quality checking of the data.
 - The Sponsor assumes accountability for actions delegated to other individuals (eg, Contract Research Organizations).
 - Study monitors will perform ongoing source data verification to confirm that data entered into the eCRF by authorized site personnel are accurate, complete, and verifiable from source documents; that the safety and rights of subjects are being protected; and that the study is being conducted in accordance with the currently approved protocol and any other study agreements, ICH GCP, and all applicable regulatory requirements.
 - Records and documents, including signed ICFs, pertaining to the conduct of this study must be retained by the Investigator per ICH-GCP and local regulations or institutional policies. No records may be destroyed during the retention period without the written approval of the Sponsor. No records may be transferred to another location or party without written notification to the Sponsor.

10.1.6. Source Documents

- Source documents provide evidence for the existence of the subject and substantiate the integrity of the data collected. Source documents are filed at the Investigator's site.
- Data entered in the eCRF that are transcribed from source documents must be consistent with the source documents or the discrepancies must be explained. The Investigator may need to request previous medical records or transfer records, depending on the study. Also, current medical records must be available.
- Source documents are original documents, data, and records from which the subject's eCRF data are obtained. These include but are not limited to hospital records, clinical and office charts, laboratory and pharmacy records, diaries, microfiches, radiographs, and correspondence.

10.1.7. Study and Site Closure

- The Sponsor designee reserves the right to close the study site or terminate the study at any time for any reason at the sole discretion of the Sponsor. Study sites will be closed upon study completion. A study site is considered closed when all required documents and study supplies have been collected and a study-site closure visit has been performed.
- The Investigator may initiate study-site closure at any time, provided there is reasonable cause and sufficient notice is given in advance of the intended termination.
- Reasons for the early closure of a study site by the Sponsor or Investigator may include but are not limited to:
 - Failure of the Investigator to comply with the protocol, the requirements of the IRB/IEC or local health authorities, the Sponsor's procedures, or GCP guidelines
 - Inadequate recruitment of subjects by the Investigator
 - Discontinuation of further IP development

10.1.8. Publication Policy

The publication policy is located within the Clinical Study Agreement with the Investigator and/or Institution.

10.2. Appendix 2: Clinical Laboratory Tests

The tests detailed in [Table 2](#) and [Table 3](#) will be performed by the central laboratory.

Protocol-specific requirements for inclusion or exclusion of subjects are detailed in [Section 5](#) of the protocol.

Additional tests may be performed at any time during the study as determined necessary by the Investigator or required by local regulations.

Investigators must document their review of each laboratory safety report in subject's source records.

Table 2: Protocol-Required Safety Laboratory Assessments

Hematology	
White blood cell count (WBC) with differential (neutrophils, lymphocytes, monocytes, eosinophils, basophils)	Red blood cell (RBC) with indices (MCV and MCH)
Hemoglobin	Hematocrit
Platelet count	
Clinical Chemistry	
Alanine aminotransferase (ALT)	Aspartate aminotransferase (AST)
Alkaline phosphatase ¹	Gamma-glutamyl transferase (GGT)
Total and direct bilirubin (fractionated)	Albumin
Calcium	Blood urea nitrogen (BUN)
Sodium	Creatinine
Chloride	Potassium
Glucose (non-fasting)	Lactic dehydrogenase (LDH)
Uric acid	Magnesium
Total protein	Total bile acid
Coagulation	
INR	
Urinalysis	
Basic urinalysis (dipstick) to be performed at the Screening visit, Week 24, and Early Discontinuation of IP/Withdrawal from Study visits. Reflex microscopic evaluation will be performed if the dipstick is abnormal.	

Other Laboratory Assessments

• Human chorionic gonadotropin (hCG) pregnancy test (as needed for women of childbearing potential)• Follicle-stimulating hormone and estradiol (as needed in women of non-childbearing potential only)• Viral hepatitis serology (hepatitis B surface antigen [HBsAg], and hepatitis C virus antibody)• Urine cotinine

¹Fractionation of ALP if ALP > 1xULN.

The additional tests listed in [Table 3](#) will be collected only as part of liver safety actions and follow up. See also Appendix 6 ([Section 10.6](#)).

Table 3: Liver Safety Laboratory Assessments

Hematology
Expanded viral hepatitis serology: 
• Hepatitis A immunoglobulin M (IgM) antibody• HBsAg and HBcAb• hepatitis C RNA• cytomegalovirus IgM antibody• Epstein-Barr viral capsid antigen IgM antibody (or if unavailable, heterophile antibody or monospot testing)• hepatitis E IgM antibody• Anti-nuclear antibody, anti-smooth muscle antibody, Type 1 anti-liver kidney microsomal antibodies, quantitative total immunoglobulin G (IgG) or gamma globulins, and serum acetaminophen
Chemistry

• Bile acids (bile acid, fractionated and total, liquid chromatography-tandem mass spectrometry (LC/MS-MS) if bile acid > 3 x ULN)• International normalized ratio (INR)• Serum creatine phosphokinase (CPK)• Lactate dehydrogenase (LDH)

10.3. Appendix 3: Adverse Events: Definitions and Procedures for Recording, Evaluating, Follow up, and Reporting

10.3.1. Definition of AE

AE Definition

• An AE is any untoward medical occurrence in a subject or clinical study subject, temporally associated with the use of IP, whether or not considered related to the IP.• NOTE: An AE can therefore be any unfavorable and unintended sign (including an abnormal laboratory finding), symptom, or disease (new or exacerbated) temporally associated with the use of IP.

Events Meeting the AE Definition

• Any abnormal laboratory test results (hematology, clinical chemistry, or urinalysis) or other safety assessments (eg, ECG, radiological scans, vital signs measurements), including those that worsen from baseline, considered clinically significant in the medical and scientific judgment of the Investigator (ie, not related to progression of underlying disease).• Exacerbation of a chronic or intermittent pre-existing condition other than the disease under study including either an increase in frequency and/or intensity of the condition.• New conditions detected or diagnosed after IP administration even though it may have been present before the start of the study.• Signs, symptoms, or the clinical sequelae of a suspected drug-drug interaction.• Signs, symptoms, or the clinical sequelae of a suspected overdose of either IP or a concomitant medication. Overdose per se will not be reported as an AE/SAE unless it is an intentional overdose taken with possible suicidal/self-harming intent. Such overdoses should be reported regardless of sequelae.• “Lack of efficacy” or “failure of expected pharmacological action” per se will not be reported as an AE or SAE. Such instances will be captured in the efficacy assessments. However, the signs, symptoms, and/or clinical sequelae resulting from lack of efficacy will be reported as AE or SAE if they fulfil the definition of an AE or SAE.

Events NOT Meeting the AE Definition

• Any clinically significant abnormal laboratory findings or other abnormal safety assessments which are associated with the underlying disease, unless judged by the Investigator to be more severe than expected for the subject's condition.• The disease/disorder being studied or expected progression, signs, or symptoms of the disease/disorder being studied, unless more severe than expected for the subject's condition.• Medical or surgical procedure (eg, endoscopy, appendectomy): the condition that leads to the procedure is the AE.• Situations in which an untoward medical occurrence did not occur (social and/or convenience admission to a hospital).• Anticipated day-to-day fluctuations of pre-existing disease(s) or condition(s) present or detected at the start of the study that do not worsen.

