8.3.6. Disease-Related Events and/or Disease-Related Outcomes Not Qualifying as AEs or SAEs

Asthma worsening is the primary efficacy endpoint and is a disease-related outcome not qualifying as an AE unless the Investigator considers asthma worsening to have met the definition of an SAE (Appendix 3; [Section 10.3.2](#)). Asthma worsening meeting the definition of an SAE will be reported in the appropriate eCRF (Appendix 3; [Section 10.3.5](#)). Asthma worsening not meeting the definition of an SAE should not be reported as an AE. Asthma worsening, as assessed by the primary efficacy endpoint and by the occurrence of SAEs, will be monitored by both the Sponsor and the IDMC on a routine basis.

[REDACTED]

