A subject who prematurely withdraws from the study without experiencing asthma worsening will be assigned asthma worsening status by Week 24 (yes/no) based on their discontinuation of study treatment and withdrawal from study reasons as summarized below in Table 2. If a subject's reason for discontinuation of study treatment or withdrawal from study is indicative of lack of efficacy or is an AE indicative of asthma worsening, a determination will be made prior to study unblinding for the interim analysis regarding whether the subject should be considered to have had asthma worsening for the primary endpoint. Otherwise, subjects who prematurely withdraw from the study will be considered to have not experienced asthma worsening for the primary endpoint.

Table 2:Criteria for determination of asthma worsening status for subjects who
prematurely withdraw from the study without experiencing asthma
worsening

Reason for Discontinuation of Study Treatment and/or Withdrawal from Study	Asthma Worsening Status Assigned (Yes/No)
Lack of Efficacy	Yes
AE where the corresponding AE PT reflects asthma worsening including 'asthma'	Yes
Death where death is due to an SAE where the corresponding SAE PT reflects asthma worsening including 'asthma'	Yes
Lost to follow-up, Non-compliance with study drug, Physician decision, Protocol deviation, Withdrawal by Subject, or Other, where further details indicate asthma, asthma worsening, lack of efficacy or prescription of or switch to a new asthma treatment	Yes
AE where the corresponding AE PT does not reflect asthma worsening	No
Death where death is due to an SAE where the corresponding PT does not reflect asthma worsening	No
Lost to follow-up, Non-compliance with study drug, Physician decision, Protocol deviation, Withdrawal by Subject, or Other, where further details do not indicate asthma, asthma worsening, lack of efficacy or prescription of or switch to a new asthma treatment	No

A bar graph of the proportion of subjects meeting the primary endpoint by treatment group and a bar graph of the proportion of subjects meeting each component of the primary endpoint by treatment group will be provided.

The primary endpoint and components will also be presented in a by-subject data listing.

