9. SAFETY EVALUATION

9.1. Adverse Events

Verbatim AE terms will be coded to a SOC and PT using the Medical Dictionary for Regulatory Activities (MedDRA) Version 21.0 or later.

All analyses of AEs will be based on the principle of treatment emergence. An AE is considered to be treatment-emergent if it has a start date on or after the date of the first dose of study treatment. In general, if the treatment emergence of an AE is not clear due to a missing or incomplete AE start date, the AE will be considered to be treatment-emergent unless the non-missing portions of the start date and the end date indicate otherwise.

In general, whenever a tabular summary of AEs is mentioned in this document, it is intended that the tabular summary is in reference to TEAEs, even though "treatment-emergent" may not be explicitly mentioned. By-subject data listings of AEs will include all events regardless of treatment emergence and TEAEs will be identified.

Counting will be by subject, not event, and at each level of summarization (e.g., any AE, SOC, and PT), with subjects experiencing more than one AE counted only once. In the summary of AEs by severity (mild, moderate, severe), subjects will be counted once at the highest severity reported at each level of summarization. AEs that are missing severity will be presented in summary tables as "Missing". AEs that are missing relationship to study treatment will be presented in summary tables as "Related".

The following summaries will be presented for the safety population:

- Overall Summary of AEs showing the number and percent of subjects with an AE; a moderate or severe AE; a severe AE; a SAE including asthma worsening-related terms; a SAE excluding asthma worsening-related terms; a treatment-related AE; a treatment-related SAE; an AE leading to discontinuation of study treatment; an AE leading to withdrawal from study; an AE resulting in death; and an AE of interest (as defined in Protocol Section 10.3.3).
- Incidence of AEs by SOC and PT
- AEs with Incidence \geq 5% in Any Treatment Group by PT
- Incidence of SAEs by SOC and PT Including Asthma Worsening-Related Terms
- Incidence of SAEs by SOC and PT Excluding Asthma Worsening-Related Terms
- Incidence of AEs by SOC, PT, and Maximum Severity
- Incidence of Treatment-Related AEs by SOC and PT
- Incidence of AEs Leading to Discontinuation of Study Treatment by SOC and PT
- Incidence of AEs Leading to Withdrawal from Study by SOC and PT
- Summary of Pruritus AEs

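### Protocol 8.3.6 and Appendix 3 disagree on when asthma worsening is an AE, and SAP 9.1 separates asthma terms only for SAEs, so the other AE totals can mix efficacy failure with safety

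*Protocol*

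**What the plan says.** **Recording rule in the body of the protocol.** Section 8.3.6 treats asthma worsening as an efficacy outcome. It allows AE-type reporting only when the SAE definition is met, and adds: "Asthma worsening not meeting the definition of an SAE should not be reported as an AE". No exception is made for severity.

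**Recording rule in Appendix 3.** Section 10.3.1 says that lack of efficacy is not in itself an AE. It continues: "However, the signs, symptoms, and/or clinical sequelae resulting from lack of efficacy will be reported as AE or SAE", subject to the condition "if they fulfil the definition of an AE or SAE". Two other entries narrow this. The list of qualifying events covers "Exacerbation of a chronic or intermittent pre-existing condition other than the disease under study". The list of non-qualifying events covers expected progression, "signs, or symptoms of the disease/disorder being studied, unless more severe than expected for the subject's condition". Section 10.3.2 then says that an event that is not an AE cannot be an SAE, and its examples include hospitalization for symptoms of the disease under study.

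**Analysis.** Incidence of treatment-emergent AEs is a secondary endpoint (protocol Section 3). The overall AE summary in SAP 9.1 has rows for "a SAE including asthma worsening-related terms; a SAE excluding asthma worsening-related terms", and there are SAE tables in both versions. The rows for any AE, moderate or severe AE, severe AE, AE leading to discontinuation of study treatment and AE leading to withdrawal have one version only. Counting is by subject.

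**Asthma AEs as stopping reasons.** SAP 8.3.1, Table 2, has a row that begins "AE where the corresponding AE PT reflects asthma worsening including". It assigns worsening status to subjects who withdraw without having met the endpoint. Protocol 9.4.1.1 makes the same provision.

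**The concern.** Two weaknesses meet here. First, sites have no single rule for part of the asthma events, and the dividing line in Appendix 3 (worse than expected for this subject) is a site judgment. Similar events may be recorded as AEs at one site and not at another. Second, whichever events are recorded, the SAP separates them out only in the SAE rows.

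The second weakness remains even if every site follows 8.3.6 exactly, because serious asthma worsening is also an AE and enters the any-AE row. Asthma worsening is the primary efficacy outcome and is planned to be more frequent on placebo. Asthma events inside a general AE rate can therefore offset a real excess of unrelated AEs on the active arms, in a secondary endpoint that also feeds the benefit-risk assessment at the interim analysis (protocol 9.5).

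**Working it through.** **Step 1. Compare the recording rules.**

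| Type of asthma worsening | 8.3.6 | Appendix 3 |
|---|---|---|
| Non-serious, as expected | Not an AE | Not an AE (10.3.1) |
| Non-serious, worse than expected | Not an AE | AE (10.3.1) |
| Expected symptoms leading to hospitalization | Report if the SAE definition is met | Not an AE, so cannot be an SAE (10.3.2) |

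The first row agrees and the other two conflict. In the third, 8.3.6 refers to 10.3.2 for the SAE definition, while 10.3.2 names hospitalization for the studied disease as an example of what is not an SAE.

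**Step 2. Trace a recorded asthma AE through SAP 9.1.** It always counts in the any-AE row. It counts in the moderate or severe and severe rows only if graded so, because protocol 10.3.4 keeps seriousness and severity apart. It counts in the discontinuation and withdrawal rows only if it caused that outcome.

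**Step 3. Can the preferred-term (PT) tables undo this?** A subject with an asthma AE and another AE appears on both PT lines but once in the total. Subtracting the asthma line would wrongly remove that subject. The non-asthma total cannot be derived from the tables.

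**Step 4. Check the design rates.** Protocol 9.2 and SAP 2.5 give 25% and 10.2% worsening, 8% dropout and about 120 per arm.

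- OR = (0.102/0.898)/(0.25/0.75) = 0.341, a 65.9% reduction in odds (stated: 66%).
- n = (z0.975 + z0.80)² × [1/(0.25×0.75) + 1/(0.102×0.898)] / ln(OR)² = 110.05 per arm.
- 110.05/0.92 = 119.6, so 120 per arm and 480 in total. The stated figure reproduces.

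The planned gap is 25 − 10.2 = 14.8 points, or about 30 against 12 subjects per 120. This check supports only the worsening rates used below; the documents give no AE rates.

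**Step 5. Illustrate the dilution.** Let b be the non-asthma AE rate on placebo, x the true excess on GB001, and f the share of worsening subjects with a recorded asthma AE in the category. All three are assumptions. f is taken as equal across arms, and asthma and other AEs as independent.

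- Placebo rate = b + f×0.25×(1−b)
- GB001 rate = (b+x) + f×0.102×(1−b−x)
- Shift in the difference = −f×[(1−b)×0.148 + x×0.102]

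Any AE, b = 50%, x = 5 points:

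| f | Placebo | GB001 | Difference |
|---|---|---|---|
| 0 | 50.0% | 55.0% | +5.0 |
| 10% | 51.25% | 55.46% | +4.2 |
| 25% | 53.12% | 56.15% | +3.0 |

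For b from 30% to 70% and x from 0 to 10 points, the shift at f = 10% runs from −0.10×(0.30×0.148) = −0.4 points to −0.10×(0.70×0.148 + 0.10×0.102) = −1.1 points. At f = 25% the same limits are −1.1 and −2.8 points.

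For a low-rate category, such as severe AEs or AEs leading to discontinuation, take b = 5% and x = 3 points. At f = 5% the rates are 6.19% and 8.47%, a difference of +2.3. At f = 10% they are 7.38% and 8.94%, a difference of +1.6.

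**Step 6. No efficacy difference.** With 25% worsening in both arms the shift is −f×x×0.25. At x = 5 points and f = 25% it is −0.3 points; at x = 0 it is zero.

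**The case against.** The strongest reply is that the two sections are close to consistent. The lack-of-efficacy sentence is conditional, the exacerbation entry excludes the disease under study, and ordinary asthma symptoms are listed as not being AEs. A reader might infer from the lack-of-efficacy sentence alone that Appendix 3 reverses 8.3.6. It does not, and the conflict is confined to the cases in Step 1.

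The reply also limits the consequences:

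- If 8.3.6 is followed, f reflects serious events only and may be small.
- Lack of efficacy is a separate withdrawal reason in protocol 7.2 and SAP Table 2, so many subjects who stop for poor control need no AE code.
- Table 2 allows asthma-coded AEs but does not show that non-serious ones are expected, since an asthma SAE would also fit its AE row.
- The PT tables show asthma terms by arm, and the planned by-subject listings would let someone recount.
- AE incidence is summarised descriptively, and the liver outputs are unaffected.

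All of this stands, and it limits the size of the point. It does not explain why a split thought necessary for SAEs stops there, and a recount from listings after unblinding is weaker than a row specified in advance.

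**Conclusion.** The point holds in limited form. Sections 8.3.6, 10.3.1 and 10.3.2 do not give one rule for worse-than-expected or serious asthma worsening. SAP 9.1 leaves recorded asthma events inside five AE categories with no version that excludes them.

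The effect on the comparison is conditional. At the planned worsening rates and the assumed b and x in Step 5, an any-AE contrast would move towards placebo by roughly 0.4 to 1.1 points if 10% of worsening subjects have an asthma AE recorded, and by 1.1 to 2.8 points if 25% do. It needs both a real efficacy difference and a non-trivial recorded share, and neither is known from the documents.

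A reader might go further and conclude that the AE tables will flatter GB001, or that the sign of a true excess would reverse. The documents do not support that. In the 50% and 55% illustration, a reversal would need an asthma AE recorded for most or all subjects who meet any worsening component, including a 0.5-point ACQ-5 rise, which both 8.3.6 and 10.3.1 rule out for ordinary worsening. Nor does serious asthma worsening enter every row; Step 2 shows where it does. This is a worthwhile clarification of a secondary safety endpoint and does not threaten the primary analysis.

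**What to change.** 1. **Protocol.** Reconcile 8.3.6, 10.3.1 and 10.3.2 into one recording rule that covers non-serious worsening that is worse than expected and serious worsening. Which rule is chosen matters less than having only one.
2. **SAP 9.1.** Present any AE, moderate or severe AE, severe AE, AE leading to discontinuation of study treatment and AE leading to withdrawal both including and excluding asthma worsening-related terms. Show both versions side by side. The excluding version alone could hide asthma deterioration on active treatment.
3. **Term list.** Write out the asthma worsening-related terms, use the same list for the SAE and AE rows, and fix it before unblinding at the interim analysis.

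The cost is a few more table rows, a term list that the SAE tables already need, and a short wording change in the protocol. No new data are required.
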